9.1.2.2.2. Spondyloarthritis Research Consortium of Canada MRI Score for Sacroiliac Joints

At Week 24 (Group B: Visit 505), an MRI of both left and right SIJ is collected. Both left and right SIJ are scored for bone marrow edema. Total SIJ Spondyloarthritis Research Consortium of Canada (SPARCC) scores can range from 0 to 72 with higher scores reflecting worse disease. Scoring will be performed by a central reader.

9.1.2.2.3. Ankylosing Spondylitis Spinal Magnetic Resonance Imaging Activity

At Week 24 (Group B: Visit 505), an MRI of the spine is collected. All 23 disco-vertebral units of the spine (from C2 to S1) are scored for bone marrow edema with a validated scoring method. Scoring will be performed by a central reader.

9.1.2.3. ASAS20, ASAS40, ASAS5/6, ASAS Partial Remission

The following ASAS domains are used to determine ASAS20, ASAS40, ASAS 5/6, and ASAS partial remission (Sieper et al. 2009; ASAS Handbook):

- 1) Patient Global (Section 9.1.2.4)
- 2) Spinal Pain (Section 9.1.2.5)
- 3) Function (Section 9.1.2.6)
- 4) Inflammation (mean of BASDAI questions 5 and 6) (Section 9.1.2.7)
- 5) CRP (Section 9.1.2.14.1)
- 6) Spinal mobility (lateral spinal flexion) (Section 9.1.2.8)

9.1.2.3.1. ASAS20

The ASAS20 response is derived from patient-reported assessments. An ASAS20 response is defined as a $\geq 20\%$ improvement and an absolute improvement from baseline (from originating

study) of ≥ 1 units (range 0 to 10) in ≥ 3 of the following 4 domains (Patient Global, Spinal Pain, Function, and Inflammation) and no worsening of $\geq 20\%$ and ≥ 1 unit (range 0 to 10) in the remaining domain.

9.1.2.3.2. ASAS40

The ASAS40 response (Anderson et al. 2001; Brandt et al. 2004; Sieper et al. 2009) is derived from patient-reported assessments. The ASAS40 is defined as a $\geq 40\%$ improvement and an absolute improvement from baseline (from originating study) of ≥ 2 units (range 0 to 10) in ≥ 3 of the following 4 domains (Patient Global, Spinal Pain, Function, and Inflammation) without any worsening in the remaining domain.

9.1.2.3.3. ASAS5/6

The ASAS5/6 includes assessment of all 6 individual ASAS domains listed above (Section 9.1.2.3) and represents improvement of $\geq 20\%$ in at least 5 domains.

9.1.2.3.4. ASAS Partial Remission

The ASAS partial remission is derived from patient-reported assessments. An ASAS partial remission is defined as a value not above 2 units (range 0 to 10, numeric rating scale [NRS]) in each of the following 4 domains: Patient Global, Spinal Pain, Function, and Inflammation.

9.1.2.4. Patient Global (Assessment of Disease Activity)

From the ASAS Handbook (Sieper et al. 2009), the patient is asked to respond to the following question: “How active was your spondylitis on average during the last week?” The answer is recorded on an NRS and is rated between “0” (not active) and “10” (very active).

9.1.2.5. Spinal Pain

From the ASAS Handbook (Sieper et al. 2009), the patient is asked to respond to the following 2 questions (on average during the last week):

1. “How much pain of your spine due to ankylosing spondylitis do you have?”
2. “How much pain of your spine due to ankylosing spondylitis do you have at night?”

The answers are recorded on an NRS and are each rated between “0” (no pain) and “10” (most severe pain). The first question is used to derive responses (i.e., ASAS40, ASAS20, and so on).

9.1.2.6. Bath Ankylosing Spondylitis Functional Index

The BASFI is a patient-reported assessment. The BASFI establishes a patient’s functional baseline and subsequent response to treatment (Calin et al. 1995). To complete the BASFI, a patient will be asked to rate the difficulty associated with 10 individual basic functional activities. Patients respond to each question using an NRS (range 0 to 10), with a higher score indicating worse functioning.

The patient’s final BASFI score is the mean of the 10 item scores completed on an NRS.

9.1.2.7. Bath Ankylosing Spondylitis Disease Activity Index

The BASDAI is a patient-reported assessment. The BASDAI is an instrument consisting of 6 questions that relate to 5 major symptoms relevant to axSpA (Garrett et al. 1994; Sieper et al. 2009): 1) Fatigue, 2) Spinal pain, 3) Peripheral arthritis, 4) Enthesitis, 5) Intensity, and 6)

Duration of morning stiffness. Patients need to score each item with a score from 0 to 10 (NRS). Higher score represents worse disease activity.

The BASDAI50 represents an improvement of $\geq 50\%$ of the BASDAI score from baseline.

9.1.2.8. Bath Ankylosing Spondylitis Metrology Index—Spinal Mobility

The Bath Ankylosing Spondylitis Metrology Index (BASMI) is a combined index comprising the following 5 clinical measurements of spinal mobility in patients with axSpA (Jenkinson et al. 1994):

- lateral spinal flexion
- tragus-to-wall distance
- lumbar flexion (modified Schrober)
- maximal intermalleolar distance
- cervical rotation

The BASMI includes these 5 measurements which are each scaled to a score of 0 to 10 depending on the result of the assessment (BASMI linear function). The average score of the 5 assessments gives the BASMI linear result (van der Heijde et al. 2008; Sieper et al. 2009).

The BASMI must be assessed by a rheumatologist or health care provider who meets the qualifications for study assessment.

9.1.2.9. Chest Expansion

While patients have their hands resting on or behind the head, the assessor will measure the chest encircled length by centimeter (cm) at the fourth intercostal level anteriorly. The difference between maximal inspiration and expiration in cm will be recorded. Two tries will be recorded. The better (larger difference) measurement of 2 tries in centimeters will be used for analyses.

The measurement of chest expansion must be assessed by a rheumatologist or health care provider who meets the qualifications for study assessment.

9.1.2.10. Occiput to Wall Distance

The patient is to make a maximum effort to touch the head against the wall when standing with heels and back against the wall (occiput). Then the distance from occiput to wall is measured. Two tries will be recorded. The better (smaller) measurement of 2 tries in centimeters will be used for analyses (Sieper et al. 2009).

The measurement of occiput to wall distance must be assessed by a rheumatologist or health care provider who meets the qualifications for study assessment.

9.1.2.11. Maastricht Ankylosing Spondylitis Enthesitis Score

The Maastricht Ankylosing Spondylitis Enthesitis Score (MASES) is an index used to measure the severity of enthesitis (Hueft-Dorenbosch et al. 2003). The MASES assesses 13 sites for enthesitis using a score of “0” for no activity or “1” for activity. Sites assessed include: costochondral 1 (right/left), costochondral 7 (right/left), spinal iliaca anterior superior (right/left), crista iliaca (right/left), spina iliaca posterior (right/left), processus spinosus L5, and Achilles

tendon proximal insertion (right/left). The MASES is the sum of all site scores (range of scores: 0 to 13), higher scores indicate more severe enthesitis.

The MASES is to be assessed by a rheumatologist or health care provider who meets study qualifications for study assessment.

9.1.2.12. SPARCC Enthesitis Score

The SPARCC enthesitis is an index used to measure the severity of enthesitis (Maksymowych et al. 2009). The SPARCC assesses 16 sites for enthesitis using a score of “0” for no activity or “1” for activity. Sites assessed include: Medial epicondyle (left/right [L/R]), Lateral epicondyle (L/R), Supraspinatus insertion into greater tuberosity of humerus (L/R), Greater trochanter (L/R), Quadriceps insertion into superior border of patella (L/R), Patellar ligament insertion into inferior pole of patella or tibial tubercle (L/R), Achilles tendon insertion into calcaneum (L/R), and Plantar fascia insertion into calcaneum (L/R).

The SPARCC is the sum of all site scores (range of scores: 0 to 16). Higher scores indicate more severe enthesitis.

The SPARCC is to be assessed by a rheumatologist or health care provider who meets study qualifications for study assessments.

9.1.2.13. Peripheral Arthritis

9.1.2.13.1. Tender Joint Count

The number of tender and painful joints will be determined by examination of 46 joints (23 joints on each side of the patient’s body). The 46 joints to be assessed and classified as tender or not tender are detailed in site training materials. Any joints that require intra-articular injections during the study (according to Section 7.7) must be excluded from evaluation from the time of the injection to the conclusion of the study.

Joint assessments will be performed by an experienced rheumatologist or skilled and trained assessor. To minimize interobserver variation, particularly during the blinded, randomized withdrawal-retreatment period (Period 2), it is recommended that the same assessor performs the tender joint count (TJC) for a given patient. Missing, replaced, ankylosed, or arthrodesed joints will be identified by the investigator and will be excluded from evaluation during the study.

The TJC data will be collected electronically.

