
	Period 1	Period 2	Period 3
Corticosteroids	
Oral corticosteroids: If on oral corticosteroids, the dose must not exceed 10 mg/day of prednisone or its equivalent at any time during the study.
 
During Period 1, treatment alterations in oral corticosteroid dose are strongly discouraged.
 
Parenteral corticosteroids (intravenous, intramuscular): Treatment with intravenous or intramuscular corticosteroids is not permitted.
 
Parenteral corticosteroids (intra-articular): Intra-articular injection of corticosteroid may be allowed on a limited basis: It is recommended that there be no more than 1 injection within any 1 year period. The joint injected must be designated along with the medication in the eCRF and must be recorded as unevaluable on the TJC/SJC assessment.
 
Inhaled and topical steroids: Regular use of inhaled or topical steroids will be permitted during any study period.
	
Group A:
 
Oral corticosteroids: Adjustments of oral corticosteroids are allowed; however the maximum dose is not to exceed 10 mg/day of prednisone or its equivalent at any time during the study.
 
Parenteral corticosteroids (intravenous, intramuscular, intra-articular): Treatment with parenteral corticosteroids is not recommended. Intra-articular injection of corticosteroid may be allowed, as needed. The joint injected must be designated along with the medication in the eCRF and must be recorded as unevaluable on the TJC/SJC assessment.
 
Inhaled and topical steroids: Regular use of inhaled or topical steroids will be permitted during any study period.
 
Group B (participating in randomized withdrawal): Same as Period 1 until they flare. Once they flare, same as patients in Group A during Period 2.
	
Group A:
 
Oral corticosteroids: Adjustments of oral corticosteroids are allowed; however the maximum dose is not to exceed 10 mg/day of prednisone or its equivalent at any time during the study.
 
Parenteral corticosteroids (intravenous, intramuscular, intra-articular): Treatment with parenteral corticosteroids is not recommended. Intra-articular injection of corticosteroid may be allowed, as needed. The joint injected must be designated along with the medication in the eCRF and must be recorded as unevaluable on the TJC/SJC assessment.
 
Inhaled and topical steroids: Regular use of inhaled or topical steroids will be permitted during any study period.
 
Group B (participating in randomized withdrawal): Same as Period 1 until they flare. Once they flare, same as patients in Group A during Period 3.

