9.1.2.13.2. Swollen Joint Count

The number of swollen joints will be determined by examination of 44 joints (22 joints on each side of the patient’s body). The 44 joints to be assessed and classified as swollen or not swollen are detailed in site training materials. Any joints that require intra-articular injections during the study (according to Section 7.7) must be excluded from evaluation from the time of the injection to the conclusion of the study.

Joint assessment is to be performed by an experienced rheumatologist or health care provider who meets the qualifications for study assessments. To minimize interobserver variation, particularly during the blinded, randomized withdrawal-retreatment period (Period 2), it is

recommended that the same assessor performs the swollen joint count (SJC) for a given patient. Missing, replaced, ankylosed, or arthrodesed joints will be identified by the investigator and will be excluded from evaluation during the study.

The SJC data will be collected electronically.

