		SPARCC enthesitis = 0	Only applies to patients with baseline SPARCC enthesitis >0 to count % of patients having SPARCC enthesitis remission.	Missing if observed value is missing.
Tender Joint Count (TJC)	
The number of tender and painful joints will be determined by examination of 46 joints (23 joints on each side of the patient’s body). The 46 joints are assessed and classified as tender or not tender.
	TJC total score	
Adjusted sum of the pain/tenderness for all 46 joints:
 $\left( \frac{\text{sum of all joints checked to be painful/tender}}{\text{number of evaluable joints}} \right) \times 46$ 
See Appendix 2 for details.
	If more than half of the joint scores are non-evaluable, the total score will be missing.
		TJC change from baseline	Calculated as: observed TJC – baseline TJC	Missing if baseline or observed

				value is missing
		TJC = 0	only applies to patients with baseline TJC > 0 to count % of patients having TJC remission.	Missing if observed value is missing
Swollen Joint Count (SJC)	The number of swollen joints will be determined by examination of 44 joints (22 joints on each side of the patient's body). The 44 joints are assessed and classified as swollen or not swollen.	SJC total score	Adjusted sum of the pain/tenderness for all 44 joints.  $\left( \frac{\text{sum of all joints checked to be swollen}}{\text{number of evaluable joints}} \right) \times 44$  See Appendix 2 for details.	If more than half of the joint scores are not evaluable, the total score will be missing.
		SJC change from baseline	Calculated as: observed SJC – baseline SJC	Missing if baseline or observed value is missing
		SJC=0	Only applies to patients with baseline SJC > 0 to count % of patients having SJC remission..	Missing if observed value is missing
Anterior Uveitis or Uveitis Flares	Eye pain or discomfort, eye redness, blurring of vision, or any other symptoms suggestive of anterior uveitis.	Event of anterior uveitis or uveitis flare	When a patient is diagnosed as anterior uveitis or uveitis flare by an ophthalmologist (for patients with no prior history), or a physician (for patients with prior history), then the Event =1, else=0.	If missing then missing

Abbreviations: Baseline = baseline from the originating study RHBV, RHBW or RHBX; CRP = C-reactive protein; IWRS = Interactive Web Response System; no. = number; NRS = numeric rating scale; Q = question; rad-axSpA = radiographic axial spondyloarthritis.

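### A patient whose only active joint is injected can be scored as recovered (TJC=0 or SJC=0), because the injected joint leaves the count until study end

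*Protocol*

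**What the plan says.** **Exclusion.** Under Protocol 9.1.2.13.1, joints requiring "intra-articular injections during the study (according to Section 7.7) must be excluded from evaluation from the time of the injection to the conclusion" (meaning study end). Protocol 9.1.2.13.2 repeats this for swollen joints: they "must be excluded from evaluation from the time of the injection to the conclusion of the study". Protocol Table RHBY.4 (Section 7.7) adds that the injected joint "must be recorded as unevaluable on the TJC/SJC assessment".

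**When injections may occur.** In Period 1, and for Group B until flare, Table RHBY.4 says: "Intra-articular injection of corticosteroid may be allowed on a limited basis", with a recommended maximum of one per year. For Group A in Periods 2 and 3, and for Group B after flare, it does not recommend parenteral corticosteroids, but continues: "Intra-articular injection of corticosteroid may be allowed, as needed".

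**Scoring.** SAP Table RHBY.6.4 defines TJC as "Adjusted sum of the pain/tenderness for all 46 joints": tender joints divided by evaluable joints, times 46. SJC is built the same way, times 44. A total is missing only when more than half of the joints cannot be evaluated. Both rows refer to Appendix 2 for details.

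**Recovery.** The TJC=0 variable "only applies to patients with baseline TJC > 0 to count % of patients having TJC remission", and SJC=0 is defined likewise. SAP Section 4 lists recovery and change in the counts as other secondary endpoints, for the Period 2 comparison and for the long-term objective.

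**Nonresponse.** In SAP 6.3.1 the triggers are unmet response criteria, missing response data and discontinuation of study treatment. SAP 6.1.3.1 and 6.10.1 add ixekizumab retreatment. The modified version for the long-term analysis (6.3.2) uses retreatment for flare and discontinuation for an adverse event or lack of efficacy. A joint injection is not mentioned.

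**The concern.** A joint that requires a steroid injection is presumably active. Excluding it avoids crediting the study drug with the steroid's effect on that joint. With a threshold at zero, however, the exclusion gives the credit in another way: the only joint that kept the patient above zero is removed, and the patient passes as a responder. The SAP treats the comparable systemic event, ixekizumab retreatment, as nonresponse.

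The zero threshold comes from the SAP. Protocol Section 4 asks for incidence and severity of peripheral arthritis; SAP Section 4 specifies recovery as a count of zero. The long-term recovery rates are most exposed. They are descriptive, have no control arm, and include Group A patients, who may be injected as needed and whose injected joints stay out of the count until the study ends.

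**Working it through.** The plan states no figure on this point, so there is none to reproduce. The check applies the SAP scoring rule directly.

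**Inputs.** 46 tender and 44 swollen joints (Protocol 9.1.2.13.1 and 9.1.2.13.2); score = active evaluable joints / evaluable joints × 46 or 44; missing if more than half are non-evaluable (SAP Table RHBY.6.4); an injected joint is non-evaluable (Protocol Table RHBY.4).

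**1. Only active joint injected.**
- TJC: 0/45 × 46 = 0. With the joint kept as active: 1/46 × 46 = 1.
- SJC: 0/43 × 44 = 0. With the joint kept as active: 1/44 × 44 = 1.

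The score is observed, not missing, so nonresponder imputation does not act on it. The patient counts as recovered until another joint becomes active. The zero comes from the exclusion; the scaling only leaves 0 at 0.

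**2. Missingness does not catch this.** With no other active joint, TJC stays 0 with up to 23 joints injected and becomes missing at 24. SJC stays 0 with up to 22 and becomes missing at 23.

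**3. Effect on the counts.** Suppose k joints are active, one is injected, and nothing else changes. TJC = (k − 1)/45 × 46:
- k = 2: 1.02 instead of 2 (−49%)
- k = 4: 3.07 instead of 4 (−23%)
- k = 10: 9.2 instead of 10 (−8%)

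For SJC with k = 2, 1/43 × 44 = 1.02 instead of 2. The error is not always downward. If the injected joint is in fact quiet and three others are active, TJC is 3/45 × 46 = 3.07 instead of 3.

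**4. Effect on a recovery rate.** Let q be the share of the denominator (baseline count above 0) who were injected and have no active joint among those still evaluated. Counting them as not recovered lowers the reported rate by q. The documents give no value for q. If q is assumed to lie between 1% and 10%, a reported rate of 60% (also assumed) becomes 59% to 50%. The true overstatement is at most q, because some injected joints will be quiet at a later visit.

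**The case against.** The strongest reply is that the governing text has not been seen. SAP Appendix 2 is titled as the algorithm for joint counts and is where a rule on injected joints would sit. A reader might infer that the plan has no such rule. The documents do not support that: the appendix is missing from the supplied text, and its content cannot be assumed either way. The readable text contains none, and Section 6.10.4, to which Table RHBY.6.5 sends the reader for response coding, holds no coding rule.

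Exposure is also limited. Parenteral steroids are not recommended for Group A. Group B before flare has injections only on a limited basis, and Section 7.7 asks these patients to keep concomitant medication unchanged in Period 2, apart from retreatment or safety reasons. This stands, and it tempers the likely size.

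Three stronger readings are tempting but not supported:
- *Bias toward no difference in Period 2.* This requires more injections on placebo before flare, on which the documents are silent. Group B enters in sustained remission, as-needed injection starts only after flare, and data after retreatment are replaced by nonresponse.
- *Recovery overstated by as much as about 10 percentage points.* Such a figure needs invented inputs, for example 15% injected × 70% with no other active joint = 10.5 points. It is then still only an upper bound.
- *Recovered at every later visit.* Any other joint becoming active ends the zero, and a zero is correct if the injected joint is truly quiet.

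Finally, these are other secondary or descriptive endpoints without multiplicity control. That also stands.

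**Conclusion.** The point holds as a scoring artefact in the rules as readable: for a patient whose only active joint is injected, the injection produces a recovery. It can inflate the long-term TJC=0 and SJC=0 rates, and it roughly halves the count for a patient with two active joints of which one is injected. The size in this trial cannot be stated, because injection frequency is not in the documents; the 1% to 10% range above is an assumption. The Period 2 effect is probably small and its direction is not known. Primary and major secondary results are unaffected, because flare is defined by ASDAS, which contains no joint count. The conclusion rests on two assumptions: that Appendix 2 holds no contrary rule, and that injected joints were active when injected.

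**What to change.** Check Appendix 2 first. If it has no rule on injected joints, amend the SAP (Table RHBY.6.4, with the coding in Section 6.10.4 or Appendix 2):

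- For TJC=0 and SJC=0, count a patient as not recovered from the time of an intra-articular injection into a joint that belongs to that count. This matches the nonresponder handling of retreatment.
- Report the number of injected patients by treatment group.
- Keep the planned exclusion and proration as a sensitivity analysis for recovery.
- For change in TJC and SJC, add a sensitivity analysis that counts injected joints as active.

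A patient-level rule is preferable to carrying forward the joint's last recorded state. Joint counts are taken at fewer visits than the patient-reported scores, so a joint that became active and was injected between assessments would be carried forward as quiet.

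The cost is SAP wording and programming, since the eCRF already records the injected joint. The downside is that the rule is conservative for a joint that stays quiet long after the injection; the sensitivity analysis for recovery shows how much this matters. The rules on when injections are allowed do not change.

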9.1.2.13.2. Swollen Joint Count

The number of swollen joints will be determined by examination of 44 joints (22 joints on each side of the patient’s body). The 44 joints to be assessed and classified as swollen or not swollen are detailed in site training materials. Any joints that require intra-articular injections during the study (according to Section 7.7) must be excluded from evaluation from the time of the injection to the conclusion of the study.

Joint assessment is to be performed by an experienced rheumatologist or health care provider who meets the qualifications for study assessments. To minimize interobserver variation, particularly during the blinded, randomized withdrawal-retreatment period (Period 2), it is

recommended that the same assessor performs the swollen joint count (SJC) for a given patient. Missing, replaced, ankylosed, or arthrodesed joints will be identified by the investigator and will be excluded from evaluation during the study.

The SJC data will be collected electronically.

